9.4.5. Resistance Analyses

The results of HBV and potentially HDV viral sequencing will be evaluated by the sponsor virologist. Relevant changes of amino acid and/or nucleic acid variations (eg, substitutions) in the HBV and/or HDV genomes will be tabulated and described. Additional exploratory characterization of the HBV and/or HDV viral sequence and phenotype may be performed and reported separately.

9.4.6. Safety Analyses

The Safety Analysis Set will be used for all safety analyses based on pooled data from Part 1 and Part 2 of the study. In addition, selected safety analyses may be reported by study part. Such descriptive analyses will be indicated in the SAP.

Safety will be evaluated by means of descriptive summaries of AEs, clinical laboratory tests, ECGs, vital signs, and physical examinations. The safety analyses will be done for each analysis phase separately (ie, study intervention phase and follow-up phase). Results will be presented in tabular format and/or graphically by intervention arm and over time, as appropriate.

Adverse Events

The verbatim terms used in the CRF by investigators to identify AEs will be coded using the Medical Dictionary for Regulatory Activities (MedDRA). Intervention-emergent AEs are AEs with onset during the intervention phase or that are a consequence of a pre-existing condition that has worsened since baseline. All reported intervention-emergent AEs will be included in the analysis. For each AE, the percentage of participants who experience at least 1 occurrence of the given event will be summarized. AEs of interest will be analyzed separately.

Frequency tabulations, listings, or participant narratives may be provided, as appropriate, for those participants who die, who discontinue study intervention due to an AE, or who experience a severe or a serious AE.

Clinical Laboratory Tests

Laboratory data will be summarized by type of laboratory test. Descriptive statistics (n, mean, SD, minimum, median, and maximum) will be calculated for each laboratory analyte for observed values and changes from baseline at each scheduled time point by intervention arm and study phase. A graphical presentation of changes from baseline over time in selected laboratory tests will be also used by intervention arm.

The laboratory abnormalities will be determined according to the criteria specified in the DAIDS Toxicity Grading Scale (see Section 10.9, Appendix 9: DAIDS Table) or in accordance with the normal ranges of the clinical laboratory if no gradings are available. The number and percentage of the participants who experience (worst) laboratory abnormalities will be tabulated by intervention arm and study phase. Shifts in toxicity grades will be cross tabulated by intervention arm and study phase.

Electrocardiogram

Electrocardiogram data will be summarized by ECG parameter. Descriptive statistics will be calculated at baseline and for observed values and changes from baseline at each scheduled time point. Frequency tabulations of the abnormalities will be made.

The ECG variables that will be analyzed are heart rate, PR interval, QRS interval, QT interval, and corrected QT (QTc) interval corrected for heart rate according to Fridericia's formula (QTcF).¹⁴

The percentage of participants with QTc interval >450 milliseconds, >480 milliseconds, or >500 milliseconds will be summarized, as will the percentage of participants with QTc interval increases from baseline >30 milliseconds or >60 milliseconds. Shifts in QTc interval categories will be cross tabulated by intervention arm and study phase.

All clinically relevant abnormalities in ECG waveform that are changes from the baseline readings will be reported (eg, changes in T-wave morphology or the occurrence of U-waves).

Vital Signs

Descriptive statistics of temperature, body weight, pulse rate, and supine SBP and DBP will be calculated for observed values and changes from baseline at each scheduled time point. The percentage of participants with values beyond clinically important limits will be summarized.

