At the time of initial protocol writing, efficacy was assessed using snapshot data through 26 March 2020. Antiviral activity data were available for 56 CHB participants who received 3 SC injections of 25 to 400 mg JNJ-3989 every 4 weeks. The antiviral activity data showed that administration of JNJ-3989 at doses of 25 to 400 mg resulted, on average, in pronounced HBsAg decline which was generally sustained at least until Day 168 (ie, 16 weeks after last dose) across all doses. No apparent dose response was observed at doses between 100 and 400 mg JNJ-3989; a numerically smaller mean decline was observed at the lower doses of 25 and 50 mg, mainly apparent after end of JNJ-3989 dosing. Treatment status (ie, virologically suppressed or not treated) did not seem to affect HBsAg changes. Other measurable serological and virological markers (HBV DNA, HBV RNA, HBeAg, hepatitis B core-related antigen [HBcrAg]) also showed responses to JNJ-3989, indicating that JNJ-3989 shows target activity on all detectable viral products. Refer to the latest IB¹⁵ for the most recent efficacy data.

Part 1 REEF-D Study Data (Study 73763989HPB2004)

Of the 22 participants with CHD enrolled into Part 1 of the REEF-D study, 17 were randomized to treatment with JNJ-3989 100 mg + NA and 5 were randomized to placebo + NA. The predefined antiviral activity criteria to start Part 2 of the study (at least 8 JNJ-3989 treated participants with ≥ 0.5 log reduction from baseline in HBsAg and HDV RNA and 4 of those with ≥ 1 log reduction in HDV RNA) were met.

The second interim analysis (IA) was performed when all Part 1 participants (N = 22) had reached Week 48 or later, or discontinued earlier.

REEF-D Safety Data at Week 48 for Part 1

At Week 48, 6/17 (35.3%) participants in the JNJ-3989 + NA arm were reported with a Grade ≥ 3 AE.

Adverse events were considered related to JNJ-3989 by the investigator in 11/17 (64.7%) participants who received JNJ-3989 + NA treatment.

Among the adverse events of special interest (AESIs) defined in the study protocol, ALT/AST elevations were reported in 13/17 (76.5%) participants in the JNJ-3989 + NA arm and no participants in the placebo + NA arm. For 2 of these 13 participants, the ALT elevation criteria according to the protocol were not met nor the discontinuation criteria for JNJ-3989. One additional participant met the ALT elevation criteria and discontinued JNJ-3989, but the event was not reported as an AE.

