An IDMC will be established for continuous monitoring of SAEs, AEs leading to discontinuation, and ALT flares. In addition, the IDMC will support the Sponsor Committee in assessing whether there is early evidence supporting antiviral activity criteria of JNJ-3989 + NA in reducing HDV replication measured by HDV RNA reduction. Before Part 1 IA1, the Sponsor Committee, who is not directly involved in the study conduct, will be involved in the unblinded review of selected efficacy and safety parameters to decide when to trigger the start of Part 2. At the time of the Part 1 IA1 (when all participants of Part 1 have completed at least Week 16 or discontinued earlier), the sponsor, including the Sponsor Committee, will become unblinded to the Part 1 data. Once Part 2 has commenced, all sponsor personnel, including the Sponsor Committee, will remain blinded to subsequent IDMC data review during the double-blind phase. During the open-label phase, all data will be unblinded. When all participants are in the open-label phase or discontinued earlier, the IDMC responsibilities will be covered by the DRC (see Sections 9.5.4 and 10.3.6).

Before Protocol Amendment 5, Part 1 and Part 2 include 3 identical phases:

- a 4-week screening phase (may be extended up to a maximum of 8 weeks^a),
- a 144-week study intervention phase (Arm 1) and 148-week study intervention phase (Arm 2). The first 52 weeks of the intervention phase are double-blind followed by 92 and 96 weeks of open-label treatment for participants in Arms 1 and 2, respectively.
- a 48-week follow-up phase.

Per Protocol Amendment 5, Part 2 will include modified phases after screening:

- a 4-week screening phase (may be extended up to a maximum of 8 weeks^a),
- for both Arm 1 and Arm 2, the double-blind 52 weeks of intervention will be followed by an open-label phase of at least 48 weeks of JNJ-3989 for all participants, including for those participants who were randomized to placebo in the intervention phase. Arm 1 will have a total minimum of 96-week intervention and Arm 2 a total minimum of 100-week intervention.
- a reduced follow-up phase (at least 24 weeks):
 - for participants who have reached FU Week 24 or later when Protocol Amendment 5 is in effect, the EOS assessments will be scheduled at the next planned visit; *OR*
 - for participants who have not reached FU Week 24 (including participants in the open-label phase) when Protocol Amendment 5 is in effect, they will enter a 24-week follow-up phase.

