- Arm 2: placebo for JNJ-3989 (SC injection Q4W) + NA qd for 52 weeks, followed by 100 mg JNJ-3989 (SC injection Q4W) + NA qd for 96 weeks (n 4; deferred active treatment arm).

NA nucleos(t)ide analog ETV, tenofovir disoproxil, or TAF. NA treatment is continued or started from Day 1 in both arms.

Part 2

Part 2 of the study will be initiated since the antiviral activity criteria in Part 1 have been met, and the results of Part 1 IA1 (when all participants of Part 1 have completed at least Week 16 or discontinued earlier) support initiation of Part 2. Cirrhotic participants will be excluded from participation in Part 2 of the study.

Approximately 30 participants co-infected with HBV and HDV will be randomized in a 4:1 ratio to Arms 1 or 2.

- Arm 1: 100 mg JNJ-3989 (SC injection Q4W) + NA qd for at least 96 weeks (approximately, n 24; immediate active treatment arm);
- Arm 2: placebo for JNJ-3989 (SC injection Q4W) + NA qd for 52 weeks, followed by 100 mg JNJ-3989 (SC injection Q4W) + NA qd for at least 48 weeks (approximately, n 6; deferred active treatment arm).

NA ETV, tenofovir disoproxil, or TAF. NA treatment is continued or started from Day 1 in both arms.

Study Details

In total across both Part 1 and Part 2, a target of approximately 50 participants, aged ≥ 18 to 65 years, co-infected with HDV and HBV will be enrolled in this study. If Part 2 is not initiated, the number of participants will be approximately 20.

Patients with HBV/HDV co-infection will be eligible regardless of HBeAg status and treatment history. Patients with compensated cirrhosis are only allowed to be enrolled in Part 1 of this study. Cirrhotic patients will be excluded from participation in Part 2 of the study.

Randomization will be stratified by:

- presence of compensated cirrhosis at screening (yes or no) (Part 1 only),
- HDV RNA testing laboratory location (China versus outside of China) (Note: All sites in China will utilize the laboratory testing in China and all sites in other countries will utilize the laboratory outside of China), and
- HBeAg status at screening (positive versus negative).

In those countries/sites where HDV testing is not part of standard of care, possible study candidates can be prescreened for HDV testing (HDV RNA and/or anti-HDV antibody) after signing a prescreening informed consent form (ICF). Results will be reviewed by the investigator to confirm if they could qualify for study participation.

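### The two-phase safety plan puts Arm 2's placebo time and its JNJ-3989 time in one column of the cumulative safety tables

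*Protocol*

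**What the plan says.** Protocol Section 9.4.6, and the same text in the Synopsis, lists the safety phases: "The safety analyses will be done for each analysis phase separately (ie, study intervention phase and follow-up phase". The list is introduced by ie, so it is closed. The columns follow: "Results will be presented in tabular format and/or graphically by intervention arm and over time, as appropriate". Within that scheme, adverse events are counted as participants with at least one occurrence, and an event is intervention-emergent if it starts during the intervention phase. Worst laboratory abnormalities, toxicity-grade shifts and QTc shifts are cross-tabulated by arm and study phase.

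Section 4.1 defines that phase: "a 144-week study intervention phase (Arm 1) and 148-week study intervention phase (Arm 2"), and "The first 52 weeks of the intervention phase are double-blind followed by 92 and 96 weeks of open-label treatment". For Part 2 under Amendment 5, "Arm 1 will have a total minimum of 96-week intervention and Arm 2 a total minimum of 100-week intervention". Arm 2 receives placebo for 52 weeks, in Part 1 "followed by 100 mg JNJ-3989 (SC injection Q4W) + NA qd for 96 weeks", and in Part 2 JNJ-3989 for at least 48 weeks. Section 6.3 likewise has open-label dosing run from Week 52 to the end of the study intervention phase.

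**The concern.** The randomised comparison of JNJ-3989 with placebo ends when Arm 2 starts JNJ-3989 at Week 52. A cumulative table by arm over the whole intervention phase sets Arm 1, always on JNJ-3989, against an Arm 2 column that is placebo at first and JNJ-3989 afterwards. Any adverse reaction that Arm 2 participants have after the switch raises the count in the column that a reader would take as the comparator.

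This matters most for ALT elevation, which Section 2.3.1.2 calls an important potential risk with a suspected causal link to JNJ-3989. In Part 1 up to Week 48, Section 2.2.3 reports that "ALT/AST elevations were reported in 13/17 (76.5%) participants in the JNJ-3989 + NA arm and no participants in the placebo + NA arm". All analyses are now descriptive (Section 9.1), so the tables themselves carry the safety message, and no test stands beside them.

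**Working it through.** **1. Length and make-up of the phase (Section 4.1).**
- Part 1: Arm 1 is 52 + 92 = 144 weeks and Arm 2 is 52 + 96 = 148 weeks. Both agree with the stated totals.
- Part 2 minimum, Arm 2: 52 + 48 = 100 weeks, as stated.

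**2. Share of the Arm 2 phase on JNJ-3989, for a participant who rolls over.**
- Part 1: 96/148 = 64.9%.
- Part 2, at the minimum: 48/100 = 48.0%.
- Pooled over the 5 Part 1 placebo participants and the approximately 6 planned in Part 2, with full roll-over: (5×96 + 6×48)/(5×148 + 6×100) = 768/1340 = 57.3%.

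**3. The Part 1 contrast before the switch (Section 2.2.3).** ALT elevations on treatment up to Week 48 occurred in 12 of 22 participants (54.5%, as stated), all on JNJ-3989. That is 12/17 = 70.6% against 0/5, a difference of 70.6 points. The adverse-event figure of 13/17 (76.5%) reconciles with this: 13 − 2 who did not meet the elevation criteria + 1 who met them but was not reported = 12.

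**4. Dilution, as scenarios.** Expected Arm 2 incidence over the whole phase = roll-over share × incidence after the switch. The remaining difference is 70.6% minus that product. The assumptions, none of which the protocol gives, are: 50–100% roll-over, 35–70.6% incidence after the switch, no elevations on placebo, and Arm 1 held at its Week 48 rate.

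| Roll-over | Incidence after switch | Arm 2 column | Difference left (points) |
|---|---|---|---|
| 50% | 35% | 17.5% | 53.1 |
| 50% | 70.6% | 35.3% | 35.3 |
| 75% | 35% | 26.2% | 44.3 |
| 75% | 70.6% | 52.9% | 17.6 |
| 100% | 35% | 35.0% | 35.6 |
| 100% | 70.6% | 70.6% | 0.0 |

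The last row corresponds to 5 × 12/17 = 3.5 participants in Part 1, or 11 × 12/17 = 7.8 over both parts.

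**5. Does another rule separate the two periods?**
- Section 9.3 analyses the Safety set by the intervention actually received, but has no rule for a participant who received placebo and then JNJ-3989.
- Section 9.4.1 sets one baseline, before the first dose on Day 1. Arm 2 changes after the switch are therefore measured across both treatments.
- For FibroScan, a footnote to the schedule in Section 1.3.1 makes Week 48 the Arm 2 baseline because of the Week 52 switch. Section 9.4.6 has no equivalent.

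**The case against.** The strongest reply is that Section 9 calls itself a general description and leaves detail to the SAP, which is not at hand. Period boundaries and emergence rules are usual SAP content. The protocol's terms also vary. The schedules of activities head their columns separately for double-blind and open-label study intervention, and one bullet in Section 4.1 speaks of participants randomised to placebo in the intervention phase, which can only mean the double-blind part. Analysis by intervention actually received, and presentation over time as appropriate, leave room for a split. The Part 1 summary in Section 2.2.3 already cuts at Week 48 and reports follow-up separately.

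These points show that a cut is feasible and perhaps intended. They do not commit the final pooled tables to one. Section 9.4.6 does more than leave detail open: it names a closed list of two phases, and Section 4.1 defines the first as containing both periods. The only item that Section 9.4.6 expressly leaves to the SAP is reporting by study part.

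Other parts of the reply limit the point, and they stand:
- Laboratory, ECG and vital-sign summaries at scheduled visits are not mixed, since each visit lies on one side of the switch.
- Adverse events of interest are analysed separately, and the flare panel adjudicates each ALT flare.
- Section 7.1 keeps some Part 2 placebo participants out of the open-label phase (HBsAg above 10,000 IU/mL, or cirrhosis at the end of the double-blind phase).
- The Part 1 rate comes from a part that admitted participants with cirrhosis. Part 2 excluded them and changed its HBsAg and HDV RNA entry criteria to lower the flare risk.

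**Conclusion.** The point holds for cumulative tables: adverse-event incidence, worst laboratory grade, and toxicity-grade and QTc shifts. As the protocol is written, the Arm 2 column in these combines placebo and JNJ-3989 time, with 48% or more of the phase on JNJ-3989 for those who roll over, and the only randomised safety contrast is diluted.

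The size is not known from the document. Under the assumptions in step 4, the 71-point difference would shrink to between about 53 and 0 points.

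A reader might infer that the ALT signal would disappear from the report. The documents do not support that. A fall to zero needs every Arm 2 participant to roll over, the Part 1 Arm 1 rate to apply unchanged to them (including a Part 2 population selected for lower risk), and no further Arm 1 participant to have a first elevation after Week 48. By-visit summaries stay clean, and the Part 1 Week 48 contrast is already on record in Section 2.2.3. Nor does the text show that the sponsor has decided to count JNJ-3989 events as placebo events; that is what follows if the two-phase rule is applied literally. Since the analyses are descriptive, no formal test is affected. The wording should still be corrected before the final pooled tables are built.

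**What to change.** In Section 9.4.6 and the Synopsis:
- Name three safety periods: double-blind (Day 1 up to the first open-label injection), open-label, and follow-up.
- Make Arm 1 versus Arm 2 comparisons in the double-blind period only.
- Report Arm 2 events after the switch as JNJ-3989 exposure, with emergence and change judged against the last value before the first JNJ-3989 injection.
- Optionally, add a column for all JNJ-3989 exposure.

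The SAP should carry the same definitions. The cost is wording and one period variable in the analysis data. No new data are needed.

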9.4.7. Other Analyses

9.4.7.1. Pharmacokinetic Analyses

Descriptive statistics (n, mean, SD, coefficient of variation [CV], geometric mean, median, minimum, and maximum) will be calculated for the plasma concentrations of JNJ-3989 (ie, JNJ-73763924 and JNJ-73763976).

Population PK analysis of concentration-time data of JNJ-73763976 and JNJ-73763924 may be performed using non-linear mixed effects modeling. Data may be combined with selected Phase 1 and/or 2 studies to support a relevant structural model. For operational reasons, a snapshot date for PK samples to be analyzed will be defined, if required. Samples collected before this date will be analyzed for JNJ-73763976 and JNJ-73763924, and may be included in the population PK analysis. Samples collected after the snapshot date will be analyzed at a later date and may be included in a population PK re-analysis when they become available after database lock. Available participant characteristics (eg, demographics, laboratory variables, genotypes) will be included in the model as necessary. Details will be given in a population PK analysis plan and results of the population PK analysis, if applied, will be presented in a separate report.

9.4.7.2. Pharmacokinetic/Pharmacodynamic Analyses

Relationships of PK parameters for JNJ-3989 (JNJ-73763976 and JNJ-73763924), with selected efficacy and safety endpoints may be evaluated and graphically displayed, if applicable.

Modeling of key PD parameters (eg, HBsAg, HDV RNA) may be performed using population PK/PD. If PK/PD modeling of key efficacy endpoints is performed, treatment effect and possible covariates may be investigated. Other biomarkers may be explored at the sponsor's discretion.

Details will be described in a population PK/PD analysis plan and results of the PK/PD analysis, if applied, will be presented in a separate report.

9.4.7.3. Immune Analyses

Descriptive statistics (n, mean, SD, CV, geometric mean, median, minimum, and maximum) may be used to describe the magnitude of the IFN- γ T-cell response or the CD4+ and CD8+ T-cell responses (expressing at least 1 cytokine such as IL-2, TNF- α or IFN- γ specific to any HBV antigen) as defined by ELISpot and/or ICS, respectively. Changes from baseline (if present) may also be tabulated for PBMCs during study intervention. The proportion (%) of patients with positive responses based on the magnitude of the IFN- γ T-cell response or the percentage of CD4+ or CD8+ T-cells expressing one of the cytokines (eg, IL-2, TNF- α or IFN- γ) for at least 1 of the HDV and HBV antigens as defined by ELISpot and/or ICS, respectively, may be determined.

9.4.7.4. Pharmacogenomic Analyses

The statistical approach for analyzing the exploratory host DNA research may depend on the objective of the analyses (efficacy, safety, and PK) and possibly relevant genes at the time of analysis. Analyses will be conducted at the sponsor's discretion, will always be under the sponsor's supervision, and results will be presented either in the clinical study report (CSR) or a separate report.

9.4.7.5. Host Biomarkers Analyses

Statistical approaches to explore correlations between clinical outcome and blood and liver biomarkers vary and depend on the different data types of the applied technology platforms, as well as on the extent of observed interindividual variability. Analyses will be conducted at the

sponsor's discretion, will always be under the sponsor's supervision, and results will be presented either in the CSR or a separate report.

9.4.7.6. Medical Resource Utilization

Medical resource utilization data will be descriptively summarized by intervention arm.

9.5. Interim Analyses

9.5.1. Interim Analyses of Study Part 1

During the double-blind phase of Part 1, 2 IAs will be conducted by the sponsor.

Part 1 IA1: One IA will be conducted after all participants of Part 1 have completed at least Week 16 (or discontinued earlier) to allow a comprehensive review of ALT elevations observed during treatment. An in-depth understanding of the kinetics of virological parameters (eg, HDV RNA, HBsAg, HBV DNA, etc) is critical to interpret the observed ALT elevations and their pattern over time, in light of preliminary understanding the benefit-risk ratio of the investigational regimen in HDV-infected participants. The sponsor will become unblinded to Part 1 efficacy and safety data for this IA to inform the decision of the Sponsor Committee for the initiation of Part 2 in conjunction with the IDMC recommendations.

From the moment of data unblinding for Part 1 IA1 onwards, the sponsor will remain unblinded to Part 1 data. The investigators, participants, site personnel, and operational sponsor team members involved with the sites will remain blinded. For safety-related decisions, HDV RNA and HBsAg data may be discussed with investigators on a case-by-case basis.

Part 1 IA2: A second IA will be conducted after all participants of Part 1 have completed at least Week 48 visit (or discontinued earlier).

9.5.2. Interim Analysis of Study Part 2

The original protocol included an IA of Part 2 when all participants had reached Week 148 (EOT or discontinued earlier). This IA of Part 2 was to be conducted to assess safety and evaluate the time course of different disease markers and to support the sponsor's interactions with health authorities. Due to the decision to reduce the study duration of Part 2 and since interactions with health authorities are no longer planned, the IA of Part 2 was removed per Protocol Amendment 5.

